5.2.3.4 Rescue Therapy

For subjects re-randomized to placebo, ABT-494 7.5 mg QD or ABT-494 15 mg QD in Period 2, blinded rescue therapy with ABT-494 30 mg QD will be provided after the first instance of a < EASI 50 response starting at the Week 20 visit (4 weeks after re-randomization into Period 2). These subjects will continue on ABT-494 30 mg QD for the remainder of the study.

During Period 2, concomitant class III – IV, medium potency topical corticosteroid treatment will be permitted at the Week 24 visit and thereafter in subjects after a second instance of < EASI 50 response in any two Period 2 study visits beginning from Week 20. For subjects who receive topical corticosteroid rescue therapy, an additional visit will be

required 4 weeks after receiving topical corticosteroid rescue therapy. Discontinuation from study drug will be mandatory for subjects with < EASI 50 response compared with their Baseline EASI score 4 weeks following rescue with topical corticosteroids or at any visit thereafter.

Topical treatment allowed is limited to up to twice daily triamcinolone acetonide 0.1% cream or up to once daily mometasone furoate 0.1% cream. Use of a topical corticosteroid treatment should be recorded on the appropriate concomitant medication eCRF.

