A qualified investigator should select the subject's right or left hand as the measuring device. For purposes of clinical estimation, the total surface of the palm plus five digits will be assumed to be approximately equivalent to 1%. Measurement of the total area of involvement by the physician is aided by imagining if scattered plaques were moved so that they were next to each other and then estimating the total area involved. The site should make every attempt to have the same qualified Investigator or designee perform all BSA assessments on a given subject throughout the study and are to be performed as specified in [Table 2](#).

Eczema Area and Severity Index (EASI)

A qualified investigator will perform the EASI assessment ([Appendix E](#)). The site should make every attempt to have the same qualified Investigator or designee perform all EASI assessments on a given subject throughout the study, following the schedule in [Table 2](#).

Investigator's Global Assessment for Atopic Dermatitis (IGA)

A qualified investigator will perform the IGA assessment ([Appendix D](#)). The site should make every attempt to have the same qualified Investigator or designee perform all IGA assessments on a given subject throughout the study and are to be performed as specified in [Table 2](#).

SCORing Atopic Dermatitis (SCORAD)

A qualified investigator will perform the SCORAD assessment ([Appendix F](#)). The site should make every attempt to have the same qualified Investigator or designee perform all

SCORAD assessments on a given subject throughout the study and are to be performed as specified in [Table 2](#); via an electronic tablet device provided to sites.

Patient Questionnaires

Subjects will complete the following questionnaires as specified in [Table 2](#):

- Dermatology Life Quality Index (DLQI) ([Appendix G](#))
- Daily Pruritus (itch) Numerical Rating Scale (NRS) ([Appendix H](#))
- Medical Outcomes Study (MOS) Sleep Scale ([Appendix I](#))
- Patient Oriented Eczema Measure (POEM) ([Appendix J](#))
- Asthma Symptoms Questionnaire (only for subjects with asthma symptoms) ([Appendix K](#))
- Daytime Nasal Symptoms Questionnaire (only for subjects with rhinitis symptoms) ([Appendix L](#))
- Atopic Dermatitis Symptom Scale (ADerm-SS) ([Appendix M](#))
- Atopic Dermatitis Impact Scale (ADerm-IS) ([Appendix N](#))
- Patient Global Impression of Severity (PGIS) ([Appendix O](#))

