- Subjects from Group 1 in Period 1: ABT-494 7.5 mg QD or matching placebo for 24 weeks
- Subjects from Group 2 in Period 1: ABT-494 15 mg QD or matching placebo for 24 weeks
- Subjects from Group 3 in Period 1: ABT-494 30 mg QD or matching placebo for 24 weeks
- Subjects from Group 4 in Period 1: ABT-494 30 mg QD or matching placebo for 24 weeks

During Period 2, starting at the Week 20 visit, subjects re-randomized to placebo, ABT-494 7.5 mg QD or ABT-494 15 mg QD will be reassigned in a blinded manner to ABT-494 30 mg QD if at any visit their response is < EASI 50. These subjects will continue on ABT-494 30 mg QD for the remainder of the study.

See Section 5.5.3 for details.

Study Drug Dispensing, Dosing, and Compliance

Study drug and Dosing Diary will be dispensed to subjects beginning at Baseline (Day 1) and as specified in Table 2. The first dose of study drug will be administered after all other Baseline (Day 1) procedures are completed. Subjects will maintain an electronic dosing diary for all study medication administered outside of the study visit, (e.g., at home) to capture dosing dates and times. At all visits, except Baseline, Week 2, 4-week follow-up visit after topical corticosteroid rescue in Period 2, and the 30-day follow-up visit, the site personnel will review the electronic diary data, returned study drug kits, and

empty study drug packaging to verify compliance. Electronic diary data stops at the Week 40 visit.

(Refer to Section 5.5 for additional information.)

Actigraphy Device

During the Screening Visit, subjects will be dispensed two actigraphy devices and will be trained on how and when to wear the devices by site staff. Subjects will be instructed to wear two actigraphy watch-type devices (one on each wrist) at bedtime daily during their whole daily rest (sleep) period (see Section 10.2 for more detail). Data will be collected from the day of the Screening visit through the Week 16 visit (see Table 2 for visits requiring data download).

5.3.1.2 Collection and Handling of Optional and Mandatory Samples for Exploratory Research and Validation Studies

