8.1.6.2 Analysis of Adverse Events

8.1.6.2.1 Treatment-Emergent Adverse Events (TEAE)

AEs will be coded using MedDRA. A TEAE is defined as an AE that began or worsened in severity after initiation of study drug.

AEs starting more than 30 days following the last dose of study drug will not be included in summaries of TEAEs.

As a general safety summary, the number and percentage of subjects experiencing TEAEs will be summarized for each treatment group for the following AE categories:

- All AEs;
- All severe AEs;
- All reasonably possibly related AEs;
- All SAEs;
- Frequent AEs (reported in 5% of subjects or more in any treatment group);
- Frequent reasonably possibly related AEs (reported in 5% of subjects or more in any treatment group);
- Discontinuations due to AEs;
- Death.

TEAEs will also be summarized separately for the period when subjects receive ABT-494 monotherapy, the period when subjects receive concomitant mometasone furoate, and the period when subjects receive concomitant triamcinolone acetonide.

Additional AEs may be considered for tabulation/summary based on recommendations from Clinical and Safety as deemed appropriate.

TEAEs will be summarized and presented by system organ classes (SOCs) and preferred terms (PTs) using MedDRA. The SOCs will be presented in alphabetical order, and the PTs will be presented in alphabetical order within each SOC.

TEAE will also be summarized by maximum severity and by maximum relationship.

- The AEs of special interest (including but not limited to serious infections, opportunistic infections, malignancy, hepatic disorder, gastrointestinal perforations, anemia, neutropenia, herpes zoster, creatine phosphokinase (CPK elevation), decreased lymphocyte counts, renal dysfunction, tuberculosis, adjudicated cardiovascular events, cardiac arrhythmias) will be summarized. Event rate (per 100 patient years) for AEs of special interest will also be summarized for the combined safety analysis of Period 1 and Period 2.

All AEs leading to discontinuation will be presented in listing format. A listing by treatment group of TEAEs grouped by SOC and MedDRA preferred term with subject identification numbers will be generated.

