#### **4.2 Design Diagram**

This is an 88-week Phase 2b, randomized, double-blind, parallel-group, placebo-controlled multicenter study of safety and efficacy of upadacitinib in adult subjects with moderate to severe AD.

The duration of the study will be up to 88 weeks and will include a 35-day maximum screening period, a 16-week double-blind treatment period (Period 1) and a 72-week double-blind treatment period (Period 2). In addition, a 30-day follow-up visit (or phone

---

call if a visit is not possible) should occur to determine the status of any ongoing AEs or serious adverse events (SAEs), or the occurrence of any new AEs/SAEs.

**Period 1:** A 16-week double-blind, placebo-controlled treatment period during which subjects will be randomized in a 1:1:1:1 ratio to one of four treatment groups:

- Group 1: upadacitinib 7.5 mg once daily (QD) for 16 weeks
- Group 2: upadacitinib 15 mg QD for 16 weeks
- Group 3: upadacitinib 30 mg QD for 16 weeks
- Group 4: Matching Placebo for 16 weeks

Randomization will be stratified by geographic region (US/PR/Canada, EU/AUS, and Japan). Enrollment in Japan will be capped at 10% of subjects (4 subjects per group).

In Period 1, discontinuation from study drug will be mandatory for any subject with an Eczema Area and Severity Index (EASI) score worsening of 25% or more compared with their baseline EASI score at any 2 consecutive scheduled study visits from Week 4 to Week 12.

**Period 2:** a 72-week double-blind, placebo controlled treatment period during which subjects who complete Period 1 will be re-randomized at Week 16 within their original treatment group assignments to either upadacitinib or placebo into a 72-week double-blind, placebo controlled treatment period in a 1:1 ratio as shown in [Figure 1](#) (study design). Randomization will be stratified by geographic region and the improvement of EASI score by at least 75% (EASI 75 response) at Week 16. At the Week 16 visit, all subjects will be re-randomized as follows into Period 2:

- Group 1 in Period 1: upadacitinib 7.5 mg QD or matching placebo for 72 weeks
  - Group 2 in Period 1: upadacitinib 15 mg QD or matching placebo for 72 weeks
  - Group 3 in Period 1: upadacitinib 30 mg QD or matching placebo for 72 weeks
-

- Group 4 in Period 1: upadacitinib 30 mg QD or matching placebo for 72 weeks

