### **Period 2:**

- Date of last dose of study drug in Period 2– Date of first dose of study drug in Period 2 + 1.
- For interim analysis at Week 32, minimum of the above and (cutoff date – Date of first dose of study drug in Period 2 + 1).

Additional summaries of upadacitinib exposures by dose level will also be performed including exposure to each dose level across periods.

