### **11.2 Analysis of Adverse Events**

Treatment-emergent adverse events (TEAEs) will be summarized in each period.

Pre-treatment adverse event and protocol-defined non SAE will be presented in a data listing. TEAEs will also be summarized separately for the time period when subjects receive upadacitinib monotherapy of each dose level across Period 1 and Period 2, the time period when subjects receive concomitant mometasone furoate, and the time period when subjects receive concomitant triamcinolone acetonide.

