### **11.2.1.7 Adverse Events by 100 Patient Years**

TEAEs will be summarized by event rate per 100 subject years, defined as

$$100 * (\text{Number of TEAEs}) / (\text{Total Patient Years})$$

where total patient years is defined as the sum of the study drug exposure (defined in Section 9.1) of all subjects normalized by 365.25, and rounded to 1 decimal place. Event rate (per 100 patient years) for AEs of special interest will also be summarized for the combined safety analysis of Period 1 and Period 2.

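### In SAP 11.2's by-dose adverse event summary, only the 30 mg column holds time after a < EASI 50 visit from Week 20; that time should also be shown separately

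*SAP*

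**What the plan says.** - **The table.** Protocol 8.1.6.2.1 plans TEAEs "summarized separately for the period when subjects receive ABT-494 monotherapy", with no mention of dose. SAP 11.2 divides this: TEAEs are "summarized separately for the time period when subjects receive upadacitinib monotherapy of each dose level across Period 1 and Period 2". SAP 9.1 supplies the matching exposure: "Additional summaries of upadacitinib exposures by dose level will also be performed including exposure to each dose level across periods". SAP 11.2.1.7 takes patient-years from SAP 9.1.
- **The design.** At the end of Period 1, subjects are "re-randomized at Week 16 within their original treatment group assignments to either upadacitinib or placebo" (SAP 4.2). Placebo subjects go to 30 mg or placebo.
- **The rescue rule.** For subjects on placebo, 7.5 mg or 15 mg in Period 2, "blinded rescue therapy with ABT-494 30 mg QD will be provided after the first instance of a < EASI 50 response" from Week 20 (Protocol 5.2.3.4). Protocol 5.3.1.1 has them "reassigned in a blinded manner to ABT-494 30 mg QD if at any visit their response is < EASI 50". They then stay on 30 mg until the study ends.
- **What can end 30 mg monotherapy.** Topical steroid is permitted, not required, after a second < EASI 50 visit and not before Week 24. Study drug must stop if topical rescue fails (Protocol 5.2.3.4). Protocol 5.4.1 also leaves withdrawal of non-responders to the investigator's discretion.
- **Who scores the trigger.** "A qualified investigator will perform the EASI assessment" (Protocol 5.3.1.1).
- **Rescue elsewhere in the SAP.** Period 2 compliance stops the day before rescue (SAP 9.2), and efficacy data after rescue are excluded (SAP 10.1.5). SAP 11.2 has no equivalent rule or footnote for adverse events by dose.

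**The concern.** The three dose columns do not share a stopping rule. For 7.5 mg and 15 mg, follow-up in the column ends when the subject meets the rescue trigger. For 30 mg it carries on, and the column also collects subjects who met the trigger on another treatment. Rates per 100 patient-years correct for unequal length of follow-up, not for which subjects and which part of their course are counted.

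After the trigger, anyone still on study drug is on 30 mg. The site, which scores EASI, can therefore work out the current dose, although the randomised arm stays masked. Relatedness is the investigator's judgement (Protocol 6.1.3), so knowing the dose could matter.

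Protocol 5.6.4 sets out to characterise dose-response, so readers will look across these columns. They could attribute to dose a difference that comes partly from post-trigger time.

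**Working it through.** **1. Trace the eight Period 2 sequences (SAP Table 1) through the rescue rule.**

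| Sequence | Before the trigger | After the trigger, if still on drug |
|---|---|---|
| 7.5/7.5 and 15/15 | 7.5 mg or 15 mg | 30 mg |
| 7.5/placebo, 15/placebo, placebo/placebo | placebo | 30 mg, started as rescue |
| 30/placebo | placebo | 30 mg, restarted as rescue |
| 30/30 and placebo/30 | 30 mg | 30 mg, continued |

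All monotherapy time after the trigger is at 30 mg. By design, none is at 7.5 mg or 15 mg.

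**2. The plan's own figures.** The documents give no rescue rate and no person-time for this table. The nearest figure is the pairwise power in Protocol 8.2 (40 per arm, SD 40, two-sided 5%). A noncentral t with 78 df gives 97.2% for a difference of 35 and 78.8% for 25, against the stated 97% and 78%. The planning values used in step 4 are therefore read correctly.

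**3. Person-weeks with a common trigger rate r.**

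From the documents: 40 per arm, 16 and 72 weeks, 1:1 re-randomisation. Assumed: full retention, one trigger time, the same r in every arm, no discretionary withdrawal. L is the number of weeks left at the trigger; T is the mean weeks on 30 mg monotherapy after it.

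- Assigned 30 mg time = 40×16 + 40×72 = 3,520.
- Subjects not on 30 mg in Period 2 = 80 on placebo + 20 on 7.5 mg + 20 on 15 mg = 120.
- 30 mg before = 3,520 − 40rL.
- 30 mg after = (40 + 120)rT = 160rT.
- Each low-dose column = 40×16 + 20×72 − 20rL = 2,080 − 20rL.

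After-trigger weeks / pooled 30 mg weeks:

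| Scenario | r = 10% | r = 25% | r = 50% |
|---|---|---|---|
| Week 20, no topical steroid (L = T = 68) | 1,088/4,336 = 25% | 2,720/5,560 = 49% | 5,440/7,600 = 72% |
| Week 20, half on topical steroid 4 weeks later (T = (68+4)/2 = 36) | 576/3,824 = 15% | 1,440/4,280 = 34% | 2,880/5,040 = 57% |
| Week 20, all on topical steroid 4 weeks later (T = 4) | 64/3,312 = 2% | 160/3,000 = 5% | 320/2,480 = 13% |
| Week 52, no topical steroid (L = T = 36) | 576/3,952 = 15% | 1,440/4,600 = 31% | 2,880/5,680 = 51% |

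With a Week 20 trigger, the 30 mg 'before' column holds 3,248, 2,840 and 2,160 weeks. Each low-dose column holds 1,944, 1,740 and 1,400.

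**4. Arm-specific illustration.** Take the Protocol 8.2 means (35, 45, 60, 70; SD 40), assume normality, and assume they apply at Week 20.

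- P(< EASI 50) = Φ((50 − mean)/40) = 0.646, 0.550, 0.401 and 0.309 for placebo, 7.5, 15 and 30 mg.
- On assigned 30 mg, 40×0.3085 = 12.34 subjects trigger, so before = 3,520 − 12.34×68 = 2,681 weeks.
- If all 80 Period 2 placebo subjects respond as placebo, 70.71 are rescued: after = (70.71 + 12.34)×68 = 5,648 weeks, or 68%.
- If they keep their Period 1 dose's response, 57.13 are rescued: after = 69.47×68 = 4,724 weeks, or 64%.
- With half on topical steroid the share is 53% or 48%; with all, 11% or 9%.

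Normality is rough: it puts 23% of the 30 mg arm above 100% improvement.

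**5. From share to rate.** If post-trigger time had k times the event rate of other time and dose had no effect, a 30 mg column with after-trigger share s would show 1 + s(k − 1) times the low-dose rate. At k = 1 there is no distortion, and k below 1 reverses it. The documents give no k.

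**The case against.** The case against is strong on four points.

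1. A reader might infer that only the 30 mg column contains < EASI 50 time. The documents do not support that. Rescue starts at Week 20, and everyone who completes Period 1 is re-randomised whatever their response. A low-dose subject below EASI 50 throughout therefore adds 16 to 20 weeks to the low-dose column. Equally, a rescued subject may respond on 30 mg and spend most of the later time above EASI 50. What is unique to 30 mg is time after a trigger at Week 20 or later.
2. The post-trigger group is mixed. A 30/placebo subject who relapsed off drug and restarted 30 mg is unlike one failing on continuous 30 mg. A single 'after' column would hide this. That stands, and the fix separates them.
3. A reader might infer that cutting 30 mg at the trigger makes the columns like-for-like. It does not. Trigger frequency may differ by dose (55%, 40% and 31% for 7.5, 15 and 30 mg in the illustration), so later 'before' time is selected differently. The 30 mg 'before' column also includes placebo/30 mg subjects first exposed at Week 16, who have no low-dose counterpart. A shared stopping rule is all that is gained.
4. The larger shares are upper-end figures. Discretionary withdrawal, mandatory stopping after failed topical rescue and steroid use all shorten post-trigger time.

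It is also true that no cross-dose test is planned on this table and that TEAEs are summarised by period as well. This limits the point's importance but does not remove it: the SAP itself divides the table by dose and gives no warning about the different stopping points.

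**Conclusion.** The asymmetry is real and follows directly from the rescue rule and the wording of SAP 11.2. The post-trigger share of the 30 mg column runs from about 2% to 72% across the common-rate scenarios (10% to 50% triggering, Week 20 or 52, none to all moving to topical steroid) and from 9% to 68% with the planning values. All of these assume 40 per arm and full retention.

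That sizes the time, not the harm. A reader might infer that 30 mg will look less safe than it is; the documents support neither a direction nor a size, and if event rates do not depend on the trigger or on dose awareness there is no distortion. Nor is there a case against the randomised Period 1 adverse event comparison, Week 16 efficacy, graded laboratory values or blinded cardiovascular adjudication. The point is a modest improvement to a supplementary, descriptive table.

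**What to change.** In SAP 11.2, and in the by-dose exposure summary of SAP 9.1:

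- Keep the pooled 30 mg column for overall exposure and rare events of special interest.
- Also show 30 mg TEAEs and exposure before and after the first < EASI 50 visit on or after Week 20, for every subject on 30 mg, including those assigned to it.
- Within 'after', separate subjects continuing 30 mg from those started or restarted on it as rescue.
- Read 'before' alongside 7.5 mg and 15 mg as sharing a stopping rule only.
- Footnote that all by-dose columns are non-randomised; that 'before' time ends at a post-randomisation outcome whose frequency may differ by dose; that 30 mg 'before' includes placebo/30 mg subjects first exposed at Week 16; and that the site can deduce the current dose after the trigger.

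The cost is one extra split of a planned table plus the footnote, using EASI scores and visit dates already collected. No protocol amendment is needed, and neither the rescue rule nor Protocol 5.5.5 changes. The downside is less 30 mg time in the cross-dose reading: for example 2,840 instead of 5,560 weeks if 25% trigger at Week 20 with no topical steroid and full retention. In the Week 20 scenarios that column is still larger than either low-dose column.

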### **11.2.1 Treatment-Emergent Adverse Events**

A treatment-emergent Adverse Event (TEAE) is defined as an adverse event with an onset or worsening date that is on or after the first dose of study drug, and no more than 30 days after the last dose of study drug.

AEs where the onset date is the same as the study drug start date are assumed to be treatment-emergent. If an incomplete onset date was collected for an adverse event, the event will be assumed to be treatment-emergent unless there is other evidence that confirms that the event was not treatment-emergent (e.g., the event end date was prior to the study drug start date).

TEAEs for the safety population in each period are defined as an event with a start date on or after the date of first study drug dose in each period and up to 30 days after the last dose of study drug in the analysis period, or prior to the date of first dose in the subsequent period for subjects who entered in to the subsequent period.

Adverse event data will be coded using the Medical Dictionary for Drug Regulatory Activities (MedDRA) version 20.0 or most up to date version.

#### **11.2.1.1 Adverse Event Overview**

The number and percentage of subjects experiencing TEAEs will be summarized for each treatment group for the following AE categories.

- Any TEAE
  - Any treatment-emergent serious adverse events (TESAE)
  - Any TEAE leading to discontinuations of study drug
-

- Any severe TEAE
- Any reasonably possibly related TEAE
- Any reasonably possibly related TESAE
- Any TEAE leading to death
- TEAEs of Special Interest
- Any Death

#### **11.2.1.2 Adverse Events by System Organ Class and Preferred Term**

TEAEs will be summarized and presented by system organ class (SOC) and preferred terms (PT). The SOCs will be presented in alphabetical order, and the PTs will be presented in alphabetical order within each SOC.

A subject who reports more than 1 AE in different SOCs will be counted only once in the overall total. A subject who reports 2 or more different PTs within the same SOC, will be counted only once in the SOC total. A subject who reports more than 1 AE with the same PT will be counted only once for that PT using the most extreme incidence.

